CRFCase Report FormCTSACenter for Translational Science ActivitiesD5W5% Dextrose in WaterDSMBData and Safety Monitoring BoardHERElectronic Health RecordFDAFood and Drug AdministrationG6PDGlucose-6-Phosphate DehydrogenaseGCPGood Clinical PracticeHIPAAHealth Insurance Portability and Accountability ActIBInvestigator's BrochureINDInvestigational New Drug ApplicationIRBInstitutional Review BoardIVIntravenousLARLegally Authorized RepresentativeLTLiver TransplantationMAOIMonoamine Oxidase Inhibitor Non-Unanticipated Problems Involving Risk to Subjects orNon-UPIRTSOOthersPHIProtected Health Information	CFR Code of Federal Regulations				
CRFCase Report FormCTSACenter for Translational Science ActivitiesD5W5% Dextrose in WaterDSMBData and Safety Monitoring BoardHERElectronic Health RecordFDAFood and Drug AdministrationG6PDGlucose-6-Phosphate DehydrogenaseGCPGood Clinical PracticeHIPAAHealth Insurance Portability and Accountability ActIBInvestigator's BrochureINDInvestigational New Drug ApplicationIRBInstitutional Review BoardIVIntravenousLARLegally Authorized RepresentativeLTLiver TransplantationMAOIMonoamine Oxidase Inhibitor Non-Unanticipated Problems Involving Risk to Subjects orNon-UPIRTSOOthersPHIProtected Health Information	cGMP Cyclic Guanosine Monophosphate				
D5W5% Dextrose in WaterDSMBData and Safety Monitoring BoardHERElectronic Health RecordFDAFood and Drug AdministrationG6PDGlucose-6-Phosphate DehydrogenaseGCPGood Clinical PracticeHIPAAHealth Insurance Portability and Accountability ActIBInvestigator's BrochureINDInvestigational New Drug ApplicationIRBInstitutional Review BoardIVIntravenousLARLegally Authorized RepresentativeLTLiver TransplantationMAOIMonoamine Oxidase Inhibitor Non-Unanticipated Problems Involving Risk to Subjects orNon-UPIRTSOOthersPHIProtected Health Information	CRF Case Report Form				
DSMBData and Safety Monitoring BoardHERElectronic Health RecordFDAFood and Drug AdministrationG6PDGlucose-6-Phosphate DehydrogenaseGCPGood Clinical PracticeHIPAAHealth Insurance Portability and Accountability ActIBInvestigator's BrochureINDInvestigational New Drug ApplicationIRBInstitutional Review BoardIVIntravenousLARLegally Authorized RepresentativeLTLiver TransplantationMAOIMonoamine Oxidase Inhibitor Non-Unanticipated Problems Involving Risk to Subjects orNon-UPIRTSOOthersPHIProtected Health Information	CTSA	Center for Translational Science Activities			
HERElectronic Health RecordFDAFood and Drug AdministrationG6PDGlucose-6-Phosphate DehydrogenaseGCPGood Clinical PracticeHIPAAHealth Insurance Portability and Accountability ActIBInvestigator's BrochureINDInvestigational New Drug ApplicationIRBInstitutional Review BoardIVIntravenousLARLegally Authorized RepresentativeLTLiver TransplantationMAOIMonoamine Oxidase Inhibitor Non-Unanticipated Problems Involving Risk to Subjects orNon-UPIRTSOOthersPHIProtected Health Information	D5W	5% Dextrose in Water			
FDAFood and Drug AdministrationG6PDGlucose-6-Phosphate DehydrogenaseGCPGood Clinical PracticeHIPAAHealth Insurance Portability and Accountability ActIBInvestigator's BrochureINDInvestigational New Drug ApplicationIRBInstitutional Review BoardIVIntravenousLARLegally Authorized RepresentativeLTLiver TransplantationMAOIMonoamine Oxidase Inhibitor Non-Unanticipated Problems Involving Risk to Subjects orNon-UPIRTSOOthersPHIProtected Health Information	DSMB	Data and Safety Monitoring Board			
G6PDGlucose-6-Phosphate DehydrogenaseGCPGood Clinical PracticeHIPAAHealth Insurance Portability and Accountability ActIBInvestigator's BrochureINDInvestigational New Drug ApplicationIRBInstitutional Review BoardIVIntravenousLARLegally Authorized RepresentativeLTLiver TransplantationMAOIMonoamine Oxidase Inhibitor Non-Unanticipated Problems Involving Risk to Subjects orNon-UPIRTSOOthersPHIProtected Health Information	HER	Electronic Health Record			
GCPGood Clinical PracticeHIPAAHealth Insurance Portability and Accountability ActIBInvestigator's BrochureINDInvestigational New Drug ApplicationIRBInstitutional Review BoardIVIntravenousLARLegally Authorized RepresentativeLTLiver TransplantationMAOIMonoamine Oxidase Inhibitor Non-Unanticipated Problems Involving Risk to Subjects orNon-UPIRTSOOthersPHIProtected Health Information	FDA	Food and Drug Administration			
HIPAAHealth Insurance Portability and Accountability ActIBInvestigator's BrochureINDInvestigational New Drug ApplicationIRBInstitutional Review BoardIVIntravenousLARLegally Authorized RepresentativeLTLiver TransplantationMAOIMonoamine Oxidase Inhibitor Non-Unanticipated Problems Involving Risk to Subjects orNon-UPIRTSOOthersPHIProtected Health Information	G6PD	Glucose-6-Phosphate Dehydrogenase			
IBInvestigator's BrochureINDInvestigational New Drug ApplicationIRBInstitutional Review BoardIVIntravenousLARLegally Authorized RepresentativeLTLiver TransplantationMAOIMonoamine Oxidase Inhibitor Non-Unanticipated Problems Involving Risk to Subjects orNon-UPIRTSOOthersPHIProtected Health Information	GCP	Good Clinical Practice			
INDInvestigational New Drug ApplicationIRBInstitutional Review BoardIVIntravenousLARLegally Authorized RepresentativeLTLiver TransplantationMAOIMonoamine Oxidase Inhibitor Non-Unanticipated Problems Involving Risk to Subjects orNon-UPIRTSOOthersPHIProtected Health Information	HIPAA	Health Insurance Portability and Accountability Act			
IRBInstitutional Review BoardIVIntravenousLARLegally Authorized RepresentativeLTLiver TransplantationMAOIMonoamine Oxidase Inhibitor Non-Unanticipated Problems Involving Risk to Subjects orNon-UPIRTSOOthersPHIProtected Health Information	IB	Investigator's Brochure			
IVIntravenousLARLegally Authorized RepresentativeLTLiver TransplantationMAOIMonoamine Oxidase Inhibitor Non-Unanticipated Problems Involving Risk to Subjects orNon-UPIRTSOOthersPHIProtected Health Information	IND	Investigational New Drug Application			
LARLegally Authorized RepresentativeLTLiver TransplantationMAOIMonoamine Oxidase Inhibitor Non-Unanticipated Problems Involving Risk to Subjects orNon-UPIRTSOOthersPHIProtected Health Information					
LTLiver TransplantationMAOIMonoamine Oxidase Inhibitor Non-Unanticipated Problems Involving Risk to Subjects orNon-UPIRTSOOthersPHIProtected Health Information	IV	Intravenous			
MAOIMonoamine Oxidase Inhibitor Non-Unanticipated Problems Involving Risk to Subjects orNon-UPIRTSOOthersPHIProtected Health Information	LAR	Legally Authorized Representative			
Non-UPIRTSONon-Unanticipated Problems Involving Risk to Subjects or OthersPHIProtected Health Information	LT	Liver Transplantation			
Non-UPIRTSOOthersPHIProtected Health Information	MAOI	Monoamine Oxidase Inhibitor			
PHI Protected Health Information		Non-Unanticipated Problems Involving Risk to Subjects or			
	Non-UPIRTSO	Others			
	PHI	Protected Health Information			
PI Principal Investigator	PI	Principal Investigator			
SAE Serious Adverse Event/Serious Adverse Experience	SAE	Serious Adverse Event/Serious Adverse Experience			
SNRI Serotonin and Norepinephrine Reuptake Inhibitor	SNRI	Serotonin and Norepinephrine Reuptake Inhibitor			
SOC Standard of Care	SOC	Standard of Care			
SOP Standard Operating Procedure	SOP	Standard Operating Procedure			
SSRI Selective Serotonin Reuptake Inhibitor	SSRI	Selective Serotonin Reuptake Inhibitor			
SVR Systemic Vascular Resistance		Systemic Vascular Resistance			
VS Vasoplegic Syndrome		Vasoplegic Syndrome			
UPIRTSO Unanticipated Problems Involving Risk to Subjects or Others	UPIRTSO	Unanticipated Problems Involving Risk to Subjects or Others			

Study Summary

Title	The Efficacy of Intravenous Hydroxocobalamin versus Methylene Blue as Treatment for Intraoperative Vasoplegic Syndrome in Liver Transplant Patients	
Running Title	Methylene Blue vs Cyanokit	
Protocol Number	18-006247	
Phase n/a		
Methodology Randomized, Open-Label		
Overall Study Duration	12 months	
Subject Participation Duration	Less than 12 hours	
Single or Multi-Site	Single Center	
Objectives	The primary aim of this study is to describe the efficacy of hydroxocobalamin vs methylene blue	
Number of Subjects	20	
Diagnosis and Main Inclusion Criteria	Patients undergoing liver transplant surgery and experiencing vasoplegia intraoperatively	
Study Product, Dose, Route, Regimen	Hydroxocobalamin (Cyanokit): 5g IV infusion over 15 minutes	
Duration of Administration	Single dose intraoperatively	
Reference therapy	Methylene blue (PROVAYBLUE TM), 2 mg/kg IV bolus administered over 15 minutes	
Statistical Methodology	This pilot study is meant to be descriptive and it aims to collect basic data for future larger study	

1 Introduction

This document is a protocol for a human research study. This study will be carried out in accordance with the applicable United States government regulations and Mayo Clinic research policies and procedures.

1.1 Background

Vasoplegic syndrome (VS) with hypotension, increased cardiac output, and low systemic vascular resistance (SVR) is a common complication during liver transplantation (LT) surgeries. Refractory hypotension often occurs after reperfusion with attenuated response to vasopressors and adequate fluid resuscitation. The development of vasoplegia greatly contributes to morbidity and mortality following LT. If the patient survives the intraoperative period, vasoplegia with prolong hypotension is associated with end-organ damages ranging from stroke, myocardial infarction, to acute renal failure. It also increases the risk of graft dysfunction after LT. Finding effective treatments for intraoperative vasoplegic syndrome my greatly improve outcomes and survival rate in patients undergoing LT.

The current clinical practice uses IV methylene blue to treat intraoperative vasoplegic syndrome in LT patients. Methylene blue has been found to increase SVR and decrease vasopressor requirements by inhibiting nitric oxide synthase. The synthase limits the generation of nitric oxide, a gasotransmitter contributing to vasoplegic syndrome. Methylene blue is also a guanylyl cyclase inhibitor, blocking the release of cyclic guanosine monophosphate (cGMP), thereby preventing vascular smooth muscle relaxation. However, methylene blue would cause inaccurate pulse oximetry reading immediately after IV administration. It also may cause a hemolytic response in patients with glucose-6-phosphate dehydrogenase (G6PD) deficiency or cause serious serotonergic syndrome when used in combination with serotonergic drugs such as selective serotonin reuptake inhibitors (SSRIs), serotonin and norepinephrine reuptake inhibitors (SNRIs), and monoamine oxidase inhibitors (MAOIs).

1.2 Investigational Agent

IV hydroxocobalamin, a form of vitamin B12, is currently approved for cyanide poison treatment. Its ability to bind and inhibit the 3 main gasotransmitters (nitric oxide, carbon monoxide, and hydrogen sulfide) contributing to vasoplegic syndrome has made it a new treatment for intraoperative vasoplegic syndrome. It is currently used as a rescue medication in methylene blue-resistance vasoplegic syndrome. In most vasoplegic cases, hydroxocobalamin is only used after methylene blue administration.

Both medications used in this study are IV liquids. methylene blue appears as clear dark blue solution. Hydroxocobalamin is a dark red crystalline powder and after reconstitution it appears as clear dark red solution.

1.3 Clinical Data to Date

A comprehensive search of the terms "hydroxocobalamin," "vitamin B12," "Cyanokit," "vasoplegia," "vasoplegic syndrome," and "liver transplantation" within MEDLINE and Embase was performed. Only 3 case reports with a total of 4 individual patients receiving B12 for the treatment of VS during LT surgeries were yielded from the MEDLINE search from 1946 to 2018 and Embase from 1988 to 2018. Although all 4 patients were reported to have favorable responses after B12 administration consistent with improved hemodynamics and reduced vasopressor requirements, no statistically significant conclusion could be drawn from the limited number of case reports.

A retrospective chart review was conducted for LT surgeries performed at our institution between January 2016 and June 2018. For patients with post-reperfusion VS treated with vasopressors, MB, and B12, hemodynamics variables and vasopressor requirements were reviewed. Fourteen of 401 LT patients during the study period presented with intraoperative VS and received vasopressors and MB as the first-line VS treatment due to the institutional protocol. Nine out of 14 patients receiving MB had an ineffective response defined as failure to improve hemodynamics or to reduce pressor requirements and were subsequently administered B12. Favorable changes in hemodynamic parameters with minimal averaged change of vasopressor requirements were observed after B12 administration. No major side-effect, medication associated complication, and post-operative mortality within 6 months of LT was observed. The institutional protocol required the usage of MB before B12 for VS treatment, causing the retrospective chart review to have clear comparison on the effectiveness of the 2 medications.

1.4 Dose Rationale

Hydroxocobalamin 5g IV infusion had been administered to effectively treat hypotension attributable to vasoplegia common in LT and cardiac surgery. Most of the case reports described using 5g IV dose in the operating room.

Intravenous methylene blue 1-2 mg/kg had been described as a therapeutic dose to treat vasodilatory shock. 2 mg/kg was found to be the most commonly used dosage from a literature review in the treatment of vasoplegic and septic shock. As the goal of this study is to find the efficacy of intravenous methylene blue as a treatment for intraoperative vasoplegic syndrome, the dosage period will be limited to a single bolus during the LT surgery. In addition to the dosage recommendation from literature search, 2 mg/kg dosage is selected due to this specific patient population. Patients undergoing LT surgery commonly experience massive blood loss and multiple blood product transfusions. A higher dosage would ensure adequate medication effect if some may be lost due to surgical blood loss.

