- The risks of hydroxocobalamin: Common side effects include increased blood pressure, erythema, rash, nausea, decreased lymphocyte count, headache, and abnormal red urine color.

2 Study Objectives

Primary Objective

To assess the efficacy of hydroxocobalamin as compared to methylene blue on improving hemodynamic stability as measured by SVR, systemic blood pressure, and amount of vasopressors administered.

Secondary Objective

The secondary end point will examine the patient outcomes in the postoperative period as measured by early tracheal extubation after surgery, length of hospital and intensive care unit stay, perioperative complications (stroke, myocardial infarction, and acute renal failure), graft function, and survival rate.

3 Study Design

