3.1 General Description

This randomized, prospective, open label, pilot study will involve 20 LT patients with intraoperative vasoplegic syndrome. If vasoplegic syndrome is identified via SVR lower than 500 dynes-sec/cm⁻⁵, the patients will be randomized to receiving either IV methylene blue or hydroxocobalamin (10 patients in each group). The administration of assigned medication will only take place once during surgery if patient is exhibiting vasoplegia after the reperfusion of the new organ as demonstrated by SVR lower than 500 dynes-sec/cm⁻⁵ sustained for a period of more than 5 minutes despite the administration of vasopressors. The primary end point will examine the efficacy of the two medications on treating intraoperative vasoplegic syndrome. The SVR, blood pressure, and amount of administrations will be recorded.

[figure not shown]
If the patients still present with vasoplegic syndrome 30 minutes after receiving IV methylene blue or hydroxocobalamin during LT surgery, the vasoplegia treatment which the patients have not received in the operating room would be utilized as life-saving measures per standard of care practice. The patients will be excluded from the comparison study, but the data of frequency of failure to effectively treat vasoplegia via certain medication may be utilized in understanding the rate of failure to provide effective treatment.

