3.4 Primary Study Endpoints

The primary endpoint of the study will be the improvement in hemodynamic values as measured by SVR, systemic blood pressure, and amount of vasopressors administered. The monitoring and documentation of hemodynamic values is part of SOC practice during LT surgery.

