4.1 Inclusion Criteria

- Age > or = 18 years old
- Patients scheduled to undergo liver transplantation
- Patients able to read and understand consent document (if patient is unable to provide an informed consent, the Legally Authorized Representative will be ask to consent on behalf of the patient).
- SVR lower than 500 dynes-sec/cm⁻⁵ sustained for more than 5 minutes despite the administration of vasopressors intraoperatively (this criterion must be met after consent intraoperatively)

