5.3 Method for Assigning Subjects to Treatment Groups

This is an open-label pilot investigation and all study participants are assigned to either of the two active treatments. There is no placebo arm in this study.

The randomization will be performed utilizing REDCap and assigned anesthesia clinical care team will be informed of patients' assigned to guide them with the selection of the assigned treatment option.

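### Sections 1.4 and 3.1 state single-drug efficacy aims that two active arms cannot deliver; some within-arm rise in SVR is expected with no drug effect, so only the comparison in Section 2 is supported.

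*Combined protocol and SAP*

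**What the plan says.** The protocol words its aim in three ways.

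- **Section 1.4 (Dose Rationale):** "the goal of this study is to find the efficacy of intravenous methylene blue as a treatment for intraoperative vasoplegic syndrome". No comparator is named, and only methylene blue is mentioned.
- **Section 3.1 (General Description):** "The primary end point will examine the efficacy of the two medications on treating intraoperative vasoplegic syndrome". This covers both drugs, again without a contrast.
- **Section 2 (Study Objectives):** "To assess the efficacy of hydroxocobalamin as compared to methylene blue on improving hemodynamic stability". This is a relative question.

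On the design, Section 5.3 states: "There is no placebo arm in this study". Allocation is randomized, ten per arm. Entry needs SVR below 500, "sustained for more than 5 minutes despite the administration of vasopressors intraoperatively" (Section 4.1).

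On the output, Section 3.4 states: "The primary endpoint of the study will be the improvement in hemodynamic values as measured by SVR, systemic blood pressure, and amount of vasopressors administered". It gives no baseline, no measurement time and no between-arm contrast. Section 7.2 plans descriptive summaries only. Section 7.1 limits the aim to feasibility and descriptive data for later work. Section 3.1 removes patients still vasoplegic at 30 minutes from the comparison, whereas Section 7.3 keeps everyone who received study drug in the primary analysis.

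**The concern.** Two active arms estimate a difference between drugs. If both arms improve alike, the data cannot separate both drugs working from neither working. The aims in Sections 1.4 and 3.1 need that separation.

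The planned tables nevertheless draw the eye to change within each arm, because the endpoint is improvement and no between-arm estimate is planned. Three things other than the study drug can raise SVR after entry: patients were selected for low readings, vasopressors are running, and the reperfusion disturbance may pass. The protocol mentions none of these as a limit on interpretation.

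Section 7.1 intends the data to inform a later study. A within-arm rise taken as a drug effect would feed that study a wrong effect size.

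**Working it through.** **1. Plan's own figure.** There is none to reproduce beyond 10 + 10 = 20. Section 7.1 says that existing information did not allow a sample size calculation.

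**2. Inputs.** From the documents: the cut of 500, more than 5 minutes of persistence, and two active arms of ten. Assumed, because the documents give no SVR distribution: true SVR with mean 800 and SD 150; independent reading noise with SD e of 50 or 75; zero drug effect.

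**3. Entry on a single low reading (upper reference, not the protocol's rule).** Let T = sqrt(150² + e²) and z = (500 − 800)/T. The expected rise is (e²/T) × φ(z)/Φ(z).

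- e = 50: T = 158.1, z = −1.897, φ/Φ = 0.0659/0.0289 = 2.28, e²/T = 15.8. Rise = 15.8 × 2.28 = 36.
- e = 75: T = 167.7, z = −1.789, φ/Φ = 0.0805/0.0368 = 2.19, e²/T = 33.5. Rise = 33.5 × 2.19 = 73.

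By simulation, 40% and 53% of these patients later read 500 or more.

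**4. Entry closer to the protocol's rule.** By simulation, keep only patients whose successive readings are all below 500, then take a fresh later reading.

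| Entry rule | Rise, e = 50 to 75 | Later at 500 or more |
|---|---|---|
| One low reading | 36 to 73 | 40 to 53% |
| Three low readings | 14 to 30 | 16 to 24% |
| Six low readings | 7 to 18 | 8 to 13% |

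Persistence shrinks the rise but does not remove it. Independent noise is the favourable case; noise that is correlated over the 5 minutes would shrink it less.

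**5. Choice of baseline (three low readings).**

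| Baseline | Rise |
|---|---|
| Lowest qualifying reading | 50 to 80 |
| Last qualifying reading | 14 to 30 |
| Mean of the qualifying readings | 14 to 30 |
| Readings taken after qualification | about 0 |

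Averaging the qualifying readings gains nothing, because all of them were selected to be low. Readings taken afterwards were not.

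**6. Dropping 30-minute failures.** With single-reading entry, removing patients still below 500 at follow-up lifts the zero-effect rise from 36–74 to 91–138. Those who remain have improved partly by construction.

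**7. The randomized contrast.** Both arms enter by the same rule, so the expected rise cancels. Simulated under zero effect, the between-arm difference was about 0 in every setting and a two-sided 5% test rejected in about 5% of trials. The contrast is imprecise: with ten per arm the 95% half-width is 2.101 × sqrt(2/10) = 0.94 SD of change, and 80% power is reached only at about 1.25 SD (normal approximation).

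**The case against.** The strongest reply is that the wording is incidental. The sentence in Section 1.4 explains why a single bolus is given. Section 3.1 is about randomizing between two drugs and goes on to call the study a comparison. The title, Study Summary and Section 2 are comparative, Section 7.1 limits the aim to description, and Section 7.2 plans no within-arm test. All of this stands, and it makes the point one of wording and reporting rather than a failure of the design. It does not remove the two sentences, and Section 7.2 offers no between-arm estimate to set against the within-arm figures.

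Four stronger readings are tempting, and the documents do not support them.

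- *The plan would declare both drugs effective if both arms rise.* No section plans that conclusion.
- *Improvement is bound to appear.* The rise is an average whose size rests on assumed variability, and the 5-minute rule cuts it. In the chart review in Section 1.3, 9 of 14 patients had an ineffective response to methylene blue.
- *The other 5 of 14 (36%) match chance recovery, and 14 of 401 (3.5%) calibrates the model.* Section 1.3 defines response by hemodynamics or pressor needs, not by SVR of 500 or more, and does not define vasoplegia there as SVR below 500. Neither figure can be used in this way.
- *The plan takes the lowest or qualifying reading as baseline.* It defines no baseline at all.

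**Conclusion.** The point holds in limited form. The design supports the relative question in Section 2 and not the single-drug aims in Sections 1.4 and 3.1. Some average within-arm rise is expected with no drug effect: about 14 to 30 dyn-s/cm5, with 16 to 24% later at 500 or more, under the assumed mean of 800, SD of 150, noise of 50 to 75 and three independent low readings. It would be 50 to 80 if the lowest reading were the baseline, and small if readings are stable. These figures illustrate the mechanism and do not predict this trial's result.

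A reader might infer that the primary comparison is biased. It is not, provided that all treated patients are kept as Section 7.3 says. The exclusion in Section 3.1 would remove that protection, because it selects patients on their outcome after randomization.

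**What to change.** 1. **Sections 1.4 and 3.1:** reword the aims to match the comparative, descriptive objective in Section 2.
2. **Section 7.2:** state that change within an arm is not evidence that either drug works. Add the between-arm difference in change, with an interval, in all treated patients.
3. **Baseline (Section 3.4 or 7.2):** define it as the mean of SVR readings taken after the 5-minute criterion is met and before the drug starts, or the last pre-dose reading if there are none. Never use the lowest reading.
4. **Sections 3.1 and 7.3:** reconcile them on patients still vasoplegic at 30 minutes, since excluding these patients inflates apparent improvement. Their frequency can still be reported by arm.

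The cost is text edits and a baseline rule on hemodynamic values that are already recorded as routine care. The downside is a narrower claim, with a wide interval at ten per arm. No change to treatment or rescue is implied.
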